9.2.2 SECONDARY OUTCOME MEASURES

- Temperature after chlorhexidine/emollient: considered both as change from before application to after application (after swabs taken in controls), change from baseline after randomisation, and as graded toxicity
 - Acquisition and loss of specific bacterial species: *Enterobacteriaceae, Acinetobacter, Staphylococcus aureus*, Group b haemolytic streptococci (A and B), Enterococcus, Candida, *Pseudomonas aeruginosa*
- SAEs

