ASSESSMENTS						D	AYS II	N TRIA	۹L		
					Week :	1			Wee	< 2	Final follow up
Face to face visit	Screening	Random-	Day	Day	Day	Day	Day	Day	Day	Day	Day 28
Face to face or telephone	D-1 to D1	isation D1	1	2	3	4	5	8	9	10-14	
Trial participation		1									
Eligibility	Х										
Parent/carer information sheet	Х										
Informed consent	Х										
Enrolment form and		X									
randomisation ^a											
Clinical assessments											
Baseline data collection ^b	X										
Weight	Х									Х	
Temperature ^c	Х		Х	Х	Х	Х	Х	Х	Х	Xi	
Skin Score ^d	X		Х	Х	Х	Х	Х	Х	Х	Xi	
Adverse Events	Х		Х	Х	Х	Х	Х	Х	Х	X ⁱ	
Microbiology											
Nose swab ^e			х		Xe			Xe			
Cervical skin fold & umbilical swabs (pooled) ^f			х		Хţ			Xf			
Rectal swab ^g			Х		Xg			Xg			
CHG ± emollient application ^h			Х	(X)	Х	(X)	Х	(X)	Х	Xi	
Final follow up											Xj

Additional explanatory notes for investigations

Intervention & assessment days are on working days – if a day falls on a non-working day then shift next activity to the closest working day, whatever the working pattern. Alternate working days are Monday, Wednesday, Friday; or Tuesday, Thursday, Saturday, depending on the standard working pattern in each country.

^a Enrolment form completed and data entered into the database. Randomisation completed electronically.

^b Includes collecting medical history, mode of delivery, birth weight, gestational age, co-morbidities and antibiotic history. ^c Temperature to be collected once at screening. Temperature to be collected BEFORE every CHG ± emollient application and 15 minutes POST application. Skin score, temperature and AEs will be monitored daily in all groups.

^dSkin to be assessed according to the skin score in Appendix I, once at screening. Skin score to be assessed BEFORE every CHG ± emollient application and 30 minutes POST application.

^e Nose swab to be taken BEFORE any CHG ± emollient application on day 1, day 3± 1 day and day 8 ± 3 days (closest working day) and at any time on this day in the control group. See Manual of Operations (MOP) for further details on how to take swabs.

^f A pooled swab of the cervical skin and umbilicus to be taken BEFORE any CHG \pm emollient application on day 1, day 3 ± 1 day and day 8 ± 3 days (closest working day) and at any time on this day in the control group. See MOP for further details on how to take swabs.

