5.3 CONTROL GROUP

5.3.1 PRODUCTS

The control group will receive routine clinical care. Any skin product which is used will be recorded on CRFs/worksheets, along with the indication for its use.

The control group will receive assessments on alternate working days, including skin score, AE and temperature assessments, as well as swabs being taken on the protocol schedule.

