6 ASSESSMENTS & FOLLOW-UP

6.1 TRIAL ASSESSMENT SCHEDULE

The trial assessment schedule is described in Table 1.

After screening, baseline data including mode of delivery, birth weight, gestational age, comorbidities, and postnatal antibiotic history will be collected. The skin will be assessed, and the baseline skin score determined.

Swabs will be taken, and temperature will be checked before each application of chlorhexidine +/emollient. After the product(s) has been applied, the body temperature should be measured after 15 minutes. A further assessment of the skin will be carried out at 30 minutes post application. Babies randomised to the control group will have swabs taken and temperature checked once on the same days as babies randomised to the alternate working day schedule.

Microbiological assessments will be performed with a nose, cervical skin fold and umbilicus (pooled) swab and a separate peri-anal swab. The timing of these swabs is described in **Table 1**, and must be taken before any application of chlorhexidine and emollient.

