6.3 PROCEDURES FOR ASSESSING SAFETY

Safety will be assessed using a modified skin score which assesses the skin condition, and presence of erythema, dryness, and any other sign of skin damage (see **Appendix I**). This will be performed before each application of chlorhexidine or emollient and 30 minutes after the product(s) application. The skin score will be considered as both an absolute value and graded. Skin score assessments will be performed once every working day on all babies to provide unbiased comparisons across randomised groups. At other times, skin score assessments will be performed as required if there is clinical concern.

In addition, temperature will be measured before, and 15 minutes after application, to monitor for hypothermia. Hypothermia will be graded as follows:

- Grade 1: 35.5 36.0C
- Grade 2: 35.4 35.0C
- Grade 3: 34.0 34.9C
- Grade 4: <34.0C

Other adverse events will be reported as described in Section 7.

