The effect of each treatment arm will be assessed within a single model with each factor being fitted independently as a factor, and not as a continuous variable. Comparison of main effects within arms will be assessed using the estimate and 95% confidence interval of the comparison of differences between factors and in comparison, to control. As this is a pilot trial, the sample size was not powered to robustly detect interactions between chlorhexidine concentrations/frequencies and emollients and so we will not test these formally, but will use exploratory analyses to assess whether there is any evidence supporting individual interactions testing each one, one at a time. As this is a pilot trial and the two co-primary outcomes capture different aspects (efficacy and safety) there will be no adjustment for multiple testing, nor for the two different bacterial load outcomes since we expect a reduction in colonisation on the skin, but potentially no change in colonisation peri-rectally.

Similar mixed models will be used to analyse change in skin temperature after vs before each application, including individual as a random effect, the change in temperature as the outcome and the pre-application (baseline) temperature as a factor. Acquisition and loss of each species will be analysed as a binary outcome variable, compared with baseline, in the relevant population (those without the species of interest at baseline, or with the species of interest at baseline, respectively).

Presence/absence of each species at each assessment will also be compared between randomised groups using mixed models, again with individual as a random effect, and with baseline presence as a factor.

Frequency of SAEs will be tabulated by randomised group, and compared using exact logistic models (or time-to-event models if AEs occur in >10% of the trial population overall). SAEs will also be tabulated by grade. Similar analyses will be conducted for the AEs in Appendix II.

A Statistical Analysis Plan will be written and approved by the Trial Management Group (TMG) and the DMC before the first interim analysis is reviewed by the DMC.

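### Controls are included in the before-to-after temperature change, but section 6.1 schedules one control reading per assessment day, so this component has no control comparison

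*Protocol*

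**What the plan says.** Section 9.2.2 makes temperature a secondary outcome with three definitions. The first is the change across an application: "considered both as change from before application to after application (after swabs taken in controls". The other two are change from baseline and graded toxicity. The bracket shows that a control value was intended for the first.

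Section 9.5 gives the analysis: "Similar mixed models will be used to analyse change in skin temperature after vs before each application", with the pre-application temperature in the model.

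On collection, section 6.1 says that control babies "will have swabs taken and temperature checked once on the same days as babies randomised to the alternate working day schedule". Table 1 note c reads "Temperature to be collected BEFORE every CHG ± emollient application and 15 minutes POST application", and section 6.3 says that "temperature will be measured before, and 15 minutes after application, to monitor for hypothermia". Both tie the pair to an application.

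Two further statements bear on which days controls are assessed. Note c has "Skin score, temperature and AEs will be monitored daily in all groups", while section 5.3.1 has "The control group will receive assessments on alternate working days, including skin score, AE and temperature assessments".

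**The concern.** The outcome definition counts controls in, and the schedule does not collect what the definition needs. If sites follow section 6.1, the reading is never taken and no later analysis plan can recover it.

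What is at stake is the interpretation of an acute temperature fall. Section 1.4.3 names a drop in body temperature as a documented effect of chlorhexidine application, and section 1.4.7 says that the control group is there so that chlorhexidine can be compared with current care. The before-to-after change is the temperature measure closest in time to the application. Without control pairs, a mean fall in the treated arms could come from the product, or equally from undressing, handling and swabbing.

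**Working it through.** No power or sample-size figure is involved. The check compares the readings that the outcome needs with the readings that the schedule provides.

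**Inputs**
- Controls: section 9.3 has 182 babies in 14 permuted blocks with one control per block, so 14 controls and 12 × 14 = 168 babies in chlorhexidine arms (14 + 168 = 182). Replacement of babies with missing swabs could add a few.
- Readings needed per occasion for a change (9.2.2, 9.5): 2.
- Readings per application in the chlorhexidine arms (Table 1 note c, 6.3): 2.
- Readings per assessment day in controls (6.1): 1.
- Swab days (Table 1 notes e to g): day 1, day 3 ± 1 and day 8 ± 3, so 3 days. Controls may be swabbed at any time on those days.

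**Pairs under section 6.1.** One reading is fewer than the two needed, so there are 0 scheduled pairs per control and 14 × 0 = 0 in all.

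**Does another section add a second reading?**
- Table 1 note c and section 6.3 attach the pair to an application, so they add nothing for controls.
- Note c's daily monitoring and section 5.3.1's alternate working days say on which days controls are assessed, not how many readings are taken in a day.
- The list of changes records that 5.3.1 was corrected to agree with 6.1, so 6.1 does not look like leftover text.

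**Can section 9.2.2 stand alone?** Suppose that its bracket requires a reading before and a reading after swabbing. Swabs fall on 3 days, so there are at most 3 pairs per control and 3 × 14 = 42 in all. No assessment section schedules them, and on other control assessment days there are no swabs to anchor an after reading. If the single reading is simply taken after swabs, the before reading is still missing.

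**For scale.** Assuming a five-day working week and a stay to day 14, a treated baby has about 2 × 5 = 10 pairs on the daily schedule and 2 × 3 = 6 on alternate days. A six-day week would give 2 × 6 = 12 on the daily schedule, and earlier discharge gives fewer.

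**The case against.** The strongest reply is that the conflict is one bracket in 9.2.2 against one sentence in 6.1. Everywhere else the pair is attached to an application, including the model in 9.5, so the rest of the protocol can be read as never meaning it for controls. The analysis plan could then say how controls enter. The first part is fair: this is an inconsistency to reconcile, not a deliberate omission. The second part does not help, because an analysis plan cannot supply a reading that was not taken.

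It can also be said that some controls will have a pair by chance. Table 1 asks for a temperature at screening, which may fall on day 1, and for another on day 1, so a control screened that day could have two readings around the first swabs. That is true, but the pair is incidental, untimed and confined to one day. The exact statement is that no pair is scheduled.

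The scope is also narrow, and this stands in full. Change from baseline and graded hypothermia need only one reading per day and can still be compared with control. Comparisons of concentration, frequency and emollient among the 12 chlorhexidine arms do not need control pairs, and choosing a regimen is the trial's stated aim in section 1.4.6.

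**Conclusion.** The inconsistency holds. As scheduled, none of the 14 controls contributes a before-to-after pair, so the control comparison cannot be estimated for one of the three definitions of one secondary outcome. At most 42 control pairs would exist under the most generous reading of 9.2.2. This assumes that sites follow section 6.1 as written and that no operating procedure outside the protocol adds a reading.

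Three stronger readings are not supported:
- A reader might infer that hypothermia cannot be compared with control at all. It can, through graded hypothermia and change from baseline.
- A reader might infer that adjusting for the pre-application value creates regression to the mean. In a randomised comparison that adjustment is a standard way of dealing with it. The loss here is the missing control for undressing, handling and swabbing.
- A reader might rank hypothermia as one of only two named safety concerns. Sections 5.2.1.2 and 7.2 also name neurological disturbance.

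The point is worth correcting because it is cheap to correct. It does not affect the co-primary outcomes.

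**What to change.** First reconcile Table 1 note c with sections 5.3.1, 6.1, 9.2.2 and 9.5 on the days when control temperature is taken, since the text now gives both daily and alternate working days.

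Then, in section 6.1 and note c, schedule two control readings on each of those days: one before and one 15 minutes after the skin check, with swabs included when due. Reword the bracket in 9.2.2 to match, so that it no longer depends on swabs being taken.

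The cost is one extra thermometer reading per assessment day in 14 babies. With a stay to day 14, that is about 6 × 14 = 84 readings on alternate working days, or 10 × 14 = 140 if daily in a five-day week.

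If this is not wanted, state in 9.2.2 and 9.5 that the before-to-after analysis is limited to the 12 chlorhexidine arms with no control comparison, and keep the control comparisons of change from baseline and graded hypothermia. That costs wording only.

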9.3 SAMPLE SIZE

The trial is designed as a permuted block factorial, with an additional control per permuted block. 182 neonates in 14 permuted blocks provides 90% power to detect a difference of 0.66 standard deviations (SDs) between concentrations and 0.47 SDs between the different levels of frequency and emollient (two-sided α =0.05) (80% power for 0.58 and 0.41 SDs, respectively). This also provides 90% power to detect a difference of 1.04 SD between each concentration and control, and 0.96 SD between each level of frequency/emollient and control (0.92 and 0.96 SDs at 80% power). Previous studies have found varying effects of chlorhexidine on log colony counts: a decrease from baseline to 24h of 0.2SD with 1% chlorhexidine in Nepal and 2SDs with 2% chlorhexidine in the USA.^{18,21}

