Interventions to be Compared	Chlorhexidine gluconate (CHG) whole body skin application in varying concentrations (2% vs 1% vs 0.5%) and varying frequency, each with or without emollient application, compared to a control group with no CHG or emollient.
Study Hypothesis	Increasing concentration and frequency of CHG skin application leads to greater reductions in bacterial colonisation. The addition of emollient improves the skin condition and safety of CHG application, permitting the more effective concentration to be used.
Primary Outcome Measure(s)	 Co-primary outcomes are: Change in bacterial load from baseline to final swab (efficacy) Adapted neonatal skin condition score (safety) (absolute score and grade)
Secondary Outcome Measure(s)	 Temperature (change in absolute temperature and grade (hypothermia)) Acquisition & loss of specific bacterial species: Enterobacteriaceae Acinetobacter Staphylococcus aureus Beta haemolytic streptococci (group A and B) Enterococcus Candida Pseudomonas aeruginosa
Randomisation	Factorial randomised controlled trial, Allocated 1:1:1:1:1:1:1:1:1:1:1:1:1 into 12 intervention arms and 1 control arm 0.5% CHG each working day with emollient

NeoCHG Protocol v2.0 29-Nov-2021

SUMMARY INFORMATION TYPE	SUMMARY DETAILS
	0.5% CHG each working day without emollient
	0.5% CHG alternate working days with emollient
	0.5% CHG alternate working days without emollient
	1% CHG each working day with emollient
	1% CHG each working day without emollient
	1% CHG alternate working days with emollient
	1% CHG alternate working days without emollient
	2% CHG each working day with emollient
	2% CHG each working day without emollient
	2% CHG alternate working days with emollient
	2% CHG alternate working days without emollient
	Control Group without emollient and without CHG
	(Alternate working days are Monday, Wednesday, Friday; or
	pattern in each country.)
Number of Participants to be	182 (babies without baseline and two post-baseline swabs on
Studied	which to assess the primary efficacy endpoint will be replaced)
Duration	12 months to complete recruitment and follow-up. Individual
	follow up during hospital admission up to day 14 after enrolment
	or discharge if earlier, and final follow up 28 days after
Funder	MRC/NIHR/DfID/Wellcome Joint Global Health Trials Call 9 – Trial Development Grant & MRC Core Funding (MRC CTU at LICL)
Chief Investigator	[name]

TRIAL ASSESSMENT SCHEDULE

TABLE 1: Trial Assessment Schedule

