3.2 PATIENT EXCLUSION CRITERIA

- 1. Poor skin condition (skin score of 2 or more in any of three domains (see Appendix I)) at the time of enrolment
- 2. Known congenital or acquired skin disorder or defect at time of enrolment
- 3. Anticipated length of hospital stay <7 days
- 4. Chlorhexidine or emollient application determined inappropriate in the opinion of the enrolling clinician

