5.4 UNBLINDING / UNMASKING

NeoCHG is an open label trial and therefore there is no unblinding/unmasking.

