9.5 ANALYSIS PLAN (BRIEF)

The analyses will be described in detail in a full Statistical Analysis Plan. This section summarises the main issues.

The primary analysis population is intention-to-treat, including all randomised babies, regardless of treatment received. This corresponds to estimating the impact of the effectiveness of the treatments. However, in secondary analyses we will also use inverse-probability weighting methods to adjust for deviation from randomised strategy, which is a more efficient approach than defining a per-protocol population.³⁹ Loss-to-follow up is expected to be low given that expected length of hospital stay under 7 days is an exclusion criteria. Therefore, most babies should have baseline and two subsequent swabs on their allocated regimen. Missing swabs will be monitored and babies without baseline and two post-baseline swabs will be replaced to maintain power. However, all baseline and post-baseline results will be included in analyses.

Analysis of the co-primary endpoints will compare within-individual differences over time across randomised arm to maximise the information gained from the trial. Analysis will use linear mixed-models, with individual as a random effect, will adjust for baseline values of each outcome, and use Normally distributed errors. Analysis will be both frequentist, enabling straightforward comparison between arms (primary analysis since sample size is based on this), and Bayesian, enabling estimation of the probability that one arm is truly superior to another. This is more powerful when sample sizes are small as use of priors provides additional information. Sensitivity analysis to prior assumptions will be performed using optimistic, non-informative and sceptical priors. Change from baseline to the single closest sample 48h post randomisation will also be done as a sensitivity analysis.

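### The site-held protocol lets staff deduce blocks of 13 with each arm once in an open-label trial, and does not say whether randomisation is stratified by hospital

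*Protocol*

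**What the plan says.** **Block structure.** Section 9.3 says "The trial is designed as a permuted block factorial, with an additional control per permuted block" and continues "182 neonates in 14 permuted blocks provides 90% power to detect a difference of 0.66 standard deviations (SDs) between concentrations". The Randomisation row of the Summary of Trial gives the ratio: "Allocated 1:1:1:1:1:1:1:1:1:1:1:1:1 into 12 intervention arms and 1 control arm".

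**Who knows what.** Section 2.1 provides each accepted site with the protocol. Section 4.1 has each allocation notified to clinical staff. Section 5.4 says "NeoCHG is an open label trial and therefore there is no unblinding/unmasking". Section 9.1 promises online randomisation with allocation concealment. Sections 4.2 and 9.1 describe blinding only for the laboratory staff who read the swabs.

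**Discretion at entry.** The fourth exclusion criterion in Section 3.2 is "Chlorhexidine or emollient application determined inappropriate in the opinion of the enrolling clinician".

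**Hospital.** Section 2 names two hospitals, one in South Africa and one in Bangladesh. Neither Section 4 nor Section 9 names a stratification factor. For the co-primary endpoints, Section 9.5 says "Analysis will use linear mixed-models, with individual as a random effect, will adjust for baseline values of each outcome, and use Normally distributed errors", and adds the treatment factors. It names neither hospital nor block, but it is headed as brief and leaves detail to a full SAP.

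**The concern.** Concealing each draw online does not stop staff inferring the next one from earlier draws when the block size is known and every allocation at their hospital is visible. A clinician who expects a particular kind of regimen could use the opinion-based exclusion, or the timing of an approach to parents, to influence which baby receives it. That is selection at entry, and reading swabs blind does not undo it. A SAP could not repair it either, because the leak lies in the document that sites hold.

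The silence on hospital matters for two reasons. It decides how far a site can track a block, and it decides whether arms, above all the 14 controls, are balanced between two hospitals that may differ in flora and practice.

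**Working it through.** **Inputs.** 182 babies, 14 blocks (Section 9.3); 13 arms in equal ratio (Summary of Trial); two hospitals (Section 2).

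**Block size.** Equal allocation to 13 arms needs blocks that are multiples of 13. Fourteen blocks of at least 13 already use 14 × 13 = 182, so every block is exactly 13 with each arm once. Hence 14 controls in total.

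**Predictability, blocks within hospital and fully tracked.** With j places left in a block, j different arms remain and the best guess is right with probability 1/j.
- Expected correct per block = 1 + 1/2 + … + 1/13 = 3.180.
- Rate = 3.180/13 = 24.5%, against 1/13 = 7.7% by chance.
- The last place (j = 1) is certain: 1 in 13, or 7.7% of allocations.
- Coarser features, by simulation: emollient class (CHG with, CHG without, control) is guessed 60% of the time against 6/13 = 46%; concentration class (three concentrations, control) 48% against 4/13 = 31%.

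**Predictability, one sequence shared by both hospitals.** Staff see only their own hospital's allocations. Guessing the arm unseen for longest is right about 10.6% of the time in simulation, against 7.7%. This is a simple rule, so a cleverer tracker might do somewhat better. No allocation is certain.

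**Balance of controls, shared sequence.** Assume each control is equally likely to come from either hospital.
- P(10:4 or worse) = 2 × [C(14,10) + … + C(14,14)]/2^14 = 2 × 1471/16384 = 0.180.
- At 10:4 the control group's hospital share is off by 10/14 − 1/2 = 0.214. A hypothetical 1 SD hospital difference, left over after baseline adjustment, would then move a control contrast by about 0.21 SD.

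**Mixing blocks of 13 and 26.** Assume both sizes are equally likely and a tracker knows the two sizes and where each block starts.
- Simulation gives about 22% correct guesses (24.5% with fixed 13) and about 2.7% strictly certain allocations (7.7%).
- After twelve different arms the thirteenth remains nearly certain to such a tracker. A block of 26 opens with twelve different arms with probability 13 × 2^12/C(26,12) = 53248/9657700 = 0.0055, so the block is a 13 with probability 1/1.0055 = 99.5%.

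**Hospital term.** Let r be the share of residual variance that hospital explains. The protocol gives no value; 5–20% is assumed.
- Unstratified: leaving hospital out multiplies the standard error by 1/√(1 − r). At r = 5%, 10%, 20% this is 1.026, 1.054, 1.118, a loss of about 3–12%.
- Stratified, r = 20%, simulated concentration contrast: the spread of the estimate is 0.190 with or without the term. Without it the model standard error is 0.212 rather than 0.189, and type I error is about 3.5%, so the test is conservative.

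**The case against.** The strongest case against runs as follows.

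- **The model.** A reader might infer that the primary model excludes hospital. The text does not support that. Section 9.5 summarises and defers to the SAP, and covariates are a usual SAP item. This objection stands, so the point is to confirm the term.
- **Predictable allocations.** A reader might also infer that 14 of the 182 allocations are known in advance. That needs blocks within hospital and staff tracking all of them, and the protocol states neither. Nor can the 24.5% be added to the 18% chance of control imbalance, because they belong to opposite designs. Both objections stand.
- **Thin route to bias.** Twelve of 13 arms receive chlorhexidine. Section 4.1 has an automatic eligibility check, Section 3 allows no exceptions, and Section 4 keeps a register of babies invited. Babies scoring 2 or more in any skin domain are excluded, and the model adjusts for baseline. These limit the harm. They do not close the route, because the fourth exclusion is a matter of opinion and emollient or concentration class is easier to guess than the exact arm.
- **The remedy.** Mixed blocks barely lower the guess rate, and newly stratifying a shared sequence makes tracking by a site easier. Both are true and are allowed for in the fix.
- **Skin scoring.** Unblinded skin scores are open to detection bias whatever the block size. That is a separate issue which these changes do not touch.

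**Conclusion.** The point holds in limited form. The block structure can be deduced exactly from the protocol that sites hold, and this undercuts the stated concealment.

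How much depends on an unstated design choice:
- **Blocks within hospital, tracked:** 24.5% correct guesses against 7.7%, and one allocation in 13 certain.
- **One shared sequence:** about 10.6% against 7.7% and none certain, but an 18% chance of a 10:4 or worse control split if the hospitals recruit equally.

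Either figure measures opportunity. The protocol gives no evidence that selection has occurred, and chance imbalance adds variability without bias on average.

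A hospital term is useful under either design: it recovers about 3–12% in standard error if allocation is unstratified, or corrects a conservative standard error if stratified. Both rest on an assumed 5–20% of residual variance, part of which baseline adjustment may already absorb.

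**What to change.** 1. Move the block structure out of Section 9.3 into a restricted randomisation document. The protocol can keep the 1:1 ratio and the total. This is the main protection, at the cost of a text amendment.
2. Because sites can already deduce 13, generate remaining allocations with randomly mixed blocks of 13 and 26 and withhold the sizes. This mainly reduces strictly certain allocations (7.7% to about 2.7%), with little effect on the overall guess rate (24.5% to about 22%). It costs one regenerated list, slightly looser balance and possibly an incomplete final block.
3. State whether randomisation is stratified by hospital. If one sequence is now shared, weigh the choice: stratifying improves balance but makes site-level tracking easier.
4. Confirm in the SAP that hospital is a fixed effect in both co-primary models. This costs one model term.

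### The detectable differences in Protocol section 9.3 do not follow from its own inputs: 0.47 SD for frequency and emollient has about 86% power, not 90%, and 0.96 SD is given at both 90% and 80% power

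*Protocol*

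**What the plan says.** Protocol section 9.3 describes the design: "The trial is designed as a permuted block factorial, with an additional control per permuted block". The trial summary gives the allocation: "Allocated 1:1:1:1:1:1:1:1:1:1:1:1:1 into 12 intervention arms and 1 control arm". Section 9.3 then states that "182 neonates in 14 permuted blocks provides 90% power" for a list of differences, at "two-sided α =0.05":

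- between concentrations, "90% power to detect a difference of 0.66 standard deviations (SDs) between concentrations", and 0.58 SD at 80%;
- between levels of the other two factors, "0.47 SDs between the different levels of frequency and emollient" at 90%, and 0.41 SD at 80%;
- each concentration against control, 1.04 SD at 90%;
- each frequency or emollient level against control, with the 80% figures for both control comparisons in brackets: "0.96 SD between each level of frequency/emollient and control (0.92 and 0.96 SDs at 80% power".

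Section 9.3 names no other alpha, no variance reduction and no correlation with baseline. Section 9.5 says that "there will be no adjustment for multiple testing", giving as its reason that the two co-primary outcomes capture different aspects, and extending this to the two bacterial load outcomes.

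**The concern.** Block count, allocation and alpha fix the group sizes and hence the detectable differences in SD units. The stated figures can therefore be checked directly, and they do not agree with the inputs printed beside them. One contradiction shows without calculation: the same comparison, at the same size and alpha, cannot have the same detectable difference at 90% and at 80% power. The repeated figure also makes the 80% value for the larger group (0.96, a frequency or emollient level against control) worse than that for the smaller group (0.92, a concentration against control).

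The trial exists to choose a regimen for a larger trial (section 1.4.6), and frequency and emollient are two of the three choices. A finding of no difference on either would be set against a design sensitivity that section 9.3 overstates on its own terms. Sections 3.3 and 9.5 also replace babies without the required swabs in order to maintain power, so the stated power has a role in conduct.

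**Working it through.** **Inputs.** 182 babies / 14 blocks = 13 per block, one per arm, so 14 per arm (section 9.3 and trial summary). Each concentration covers 4 arms: 4 × 14 = 56. Each level of frequency, and each level of emollient, covers 6 arms: 6 × 14 = 84. Controls: 14. Two-sided alpha 0.05. SD = 1, since differences are in SD units.

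**Formula.** In the normal approximation the detectable difference is d = (1.960 + z) × √(1/n₁ + 1/n₂), with z = 1.282 for 90% and 0.842 for 80% power. The t columns below use the two-sample noncentral t distribution.

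**The plan's own figure, 0.47 SD at 90%, 84 v 84.** √(1/84 + 1/84) = 0.1543. Power at 0.47 SD: 0.47/0.1543 − 1.960 = 1.086, giving 86.1% (t: 85.7%). Power at 0.41 SD: 0.41/0.1543 − 1.960 = 0.697, giving 75.7% (t: 75.2%). The detectable differences are 3.242 × 0.1543 = 0.50 SD at 90% and 2.802 × 0.1543 = 0.43 SD at 80% (t: 0.503 and 0.435). Having 0.47 SD at 90% needs about 96 per level, that is 16 blocks or 208 babies.

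**All eight figures.**

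| Comparison | Groups | Stated 90% / 80% | Recomputed (t) 90% / 80% | Power at the stated figures (t) |
|---|---|---|---|---|
| Concentrations | 56 v 56 | 0.66 / 0.58 | 0.618 / 0.534 | 93.3% / 86.0% |
| Frequency or emollient | 84 v 84 | 0.47 / 0.41 | 0.503 / 0.435 | 85.7% / 75.2% |
| Concentration v control | 56 v 14 | 1.04 / 0.92 | 0.983 / 0.849 | 92.9% / 85.9% |
| Frequency or emollient v control | 84 v 14 | 0.96 / 0.96 | 0.945 / 0.817 | 90.9% / 90.9% |

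Only 0.47 and 0.41 overstate power. The 0.96 at 90% roughly holds. As an 80% figure it is wrong.

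**Can one other assumption explain the set?**

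- *Counting controls in a factor level.* 91 v 91 gives 88.4% at 0.47 SD and 78.5% at 0.41 SD; 84 v 98 gives 88.2% and 78.3%. These come closer, but controls belong to neither frequency level, section 9.3 compares them separately, and the other figures stay unexplained.
- *A smaller SD, for instance from baseline adjustment, at one alpha.* This scales every figure by the same factor. With equal groups the ratio of the two detectable differences must be about √(84/56) = 1.22. The stated ratio is 0.66/0.47 = 1.40.
- *More or fewer blocks at alpha 0.05.* No number from 10 to 18 reproduces all the figures.

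**What does reproduce the set.** Use alpha 0.05/3 for the concentration comparisons (with each other and with control), 0.05 for frequency and emollient, and 0.05/2 for these against control. Two versions then fit (90% / 80%):

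| Comparison | 14 blocks, SD × 0.935 | 16 blocks, SD unchanged | Stated |
|---|---|---|---|
| Concentrations | 0.658 / 0.579 | 0.657 / 0.579 | 0.66 / 0.58 |
| Frequency or emollient | 0.470 / 0.407 | 0.470 / 0.406 | 0.47 / 0.41 |
| Concentration v control | 1.049 / 0.924 | 1.047 / 0.921 | 1.04 / 0.92 |
| Frequency or emollient v control | 0.964 / 0.843 | 0.962 / 0.842 | 0.96 / 0.96 |

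Seven of the eight agree to within 0.01. The eighth would be 0.84, where the text repeats 0.96. The two versions cannot be told apart, because √(14/16) = 0.935. Both need alphas that section 9.3 does not state.

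**The case against.** The strongest defence is that the planned analysis is not an unadjusted two-sample t-test. Section 9.5 specifies linear mixed models adjusted for baseline, with two post-baseline swabs per baby. If SD in section 9.3 means the raw outcome SD, an assumed baseline correlation r multiplies it by √(1 − r²). Even with a single post-baseline value, power for 0.47 SD at 84 v 84 is then 87% at r = 0.2, 90% at r = 0.36 and 94% at r = 0.5. A reader might infer from the arithmetic that the trial lacks the claimed sensitivity, or that the figures were carried over from a 208-baby design. The documents establish neither: 14 blocks with a modest variance reduction fit exactly as well as 16 blocks.

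This limits what can be concluded but does not rescue the paragraph. The defence needs two undeclared assumptions, departs from the single alpha that section 9.3 states, and still leaves the repeated 0.96.

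A reader might also take the no-adjustment sentence in section 9.5 as ruling out corrected alphas for pairwise comparisons. Its stated reason concerns multiple outcomes, so it does not settle that. The single alpha of 0.05 in section 9.3 is the firmer ground.

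On importance, the shortfall is about 0.03 SD, results are to be reported as estimates with 95% confidence intervals, and the earlier effects cited in section 9.3 range from 0.2 to 2 SD. All of that stands, and it keeps the point small in size.

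**Conclusion.** The point holds as an error in the stated figures. On the inputs that section 9.3 gives, power for frequency and emollient is about 86% where 90% is claimed and about 75% where 80% is claimed. The repeated 0.96 SD is wrong under any method; on the stated inputs the 80% value is about 0.82 SD. The figures for concentrations, and for concentration against control, do not reproduce but are conservative.

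The 86% and 75% rest on 14 babies per arm, two-sided alpha 0.05 and an SD that is already that of the analysed quantity. If the SD is the raw one and baseline adjustment is counted, actual power could reach or pass 90%. That remains open until the basis is declared. The impossibility of the repeated 0.96 rests on no such assumption.

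**What to change.** Correct the repeated 0.96 and restate section 9.3 on one declared basis. For 182 babies in 14 blocks at unadjusted two-sided alpha 0.05, in SD units and rounded up so that nominal power is met:

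| Comparison | 90% power | 80% power |
|---|---|---|
| Concentrations | 0.62 | 0.54 |
| Frequency; emollient | 0.51 | 0.44 |
| Concentration v control | 0.99 | 0.85 |
| Frequency or emollient level v control | 0.95 | 0.82 |

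If corrected alphas or a baseline-adjusted SD were intended, state each alpha, say which SD is meant, give the assumed correlation, and recompute all eight figures on that basis.

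The cost is one reworded paragraph. Enrolment and procedures do not change. On the unadjusted basis the figures for frequency and emollient become slightly less favourable and the other comparisons slightly more favourable.
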